RESEARCH PROTOCOL

Date	4/6/2022
Title	Evaluation of providing coffee to patients postoperatively to
	decrease length of stay in the PACU
Principal Investigator	[name], BSN, RN, CNOR
Sub-Investigators	[name], BSN, RN; [name], BSN, RN-BC; [name] RN, RNC-MNN; [name], BSN, RN, CGRN;
	[name], MSN, RN, CPAN
Research Specialist	[name], RN, CPN
Department	Bethesda North Minimally Invasive Surgery Center; Bethesda
	Surgery Center
Hatton #	18-050

Purpose of Study

The purpose of the study is to determine if providing coffee to patients who self-identify as coffee drinkers postoperatively will decrease the length of stay in the post-anesthesia care unit (PACU). Decreasing the length of stay in PACU for surgical patient is a pertinent outcome. The shorter length of stay can achieve higher patient engagement scores, while simultaneously increasing the productivity of the unit. This is achieved by making more beds available for new patients coming from the operating room (OR). One thought was that coffee would benefit our patients experience through a number of pathways. Initially, the stimulant effect of coffee would create a more alert patient. A more alert patient is more likely to comprehend home care instruction and be ready for discharge earlier. Coffee is often used as a remedy for morning sickness. Ideally the act of drinking coffee or even smelling the coffee may decrease the occurrence of Post-Operative Nausea and Vomiting (PONV) in our patient population. Finally, patients frequently state that the inability to drink their morning coffee is often more difficult than not being able to eat prior to surgery. By allowing those to drink coffee in PACU this would make the patient feel that they are being cared for on an emotional level, in addition to a physical level.

Hypothesis or Research Question

Primary Hypothesis:

Hypothesis 1: Patients who self-identify as coffee drinkers who receive coffee postoperatively will experience a shorter length of stay in the PACU compared to patients who self-identify as coffee drinkers and do not receive coffee postoperatively.

Secondary Hypotheses:

Hypothesis 2: Patients who self-identify as coffee drinkers who receive coffee postoperatively will experience a lower occurrence of postoperative nausea and vomiting in the PACU compared to patients who self-identify as coffee drinkers and do not receive coffee postoperatively.

Hypothesis 3: Patients who self-identify as coffee drinkers who receive coffee postoperatively will report higher patient satisfaction compared to patients who self-identify as coffee drinkers and do not receive coffee postoperatively.

Background

After performing a thorough review of the literature, no studies were found that examined whether there are benefits of drinking coffee for post-operative patients. There have been a few studies that have demonstrated a benefit of three times daily coffee consumption following abdominal surgeries. In a study of 80 patients undergoing elective open or laproscopic colectomy, Muller and colleagues (2012) found that patients who consumed 100mL of coffee three times daily, compared to patients assigned to consume 100mL of water three times daily, had a significantly shorter time to first bowel movement. Similarly, Gungorduk and colleagues (2017) studied 114 patients who were undergoing total abdominal hysterectomy and systematic paraaortic lymphadenectomy and found that compared to a group assigned to drink water, those patients assigned to consume coffee 3 times daily postoperatively, had a shorter time to bowel motility and ability to tolerate food. While these studies demonstrate that coffee consumption was tolerated after surgery, they do not provide evidence about the effectiveness of coffee consumption on length of stay and/or postoperative nausea and vomiting in the PACU.

Theoretically, coffee consumption is associated with increased brain function. "Coffee is also well-known for its positive effects on mental alertness and psychological lift, benefits often attributed to caffeine content. Indeed, frequent low doses of caffeine counter the effects of extended wakefulness" (Taylor & Demming-Adams, 2007). Additionally, Warner and colleagues (2018) state that murine models have demonstrated an enhanced speed of recovery from general anesthesia, however this phenomenon has not been examined in humans. Therefore, Warner's team (2018) conducted one of the first (if only) studies examining the association between caffeine administration and changes in sedation scores among 151 heavily sedated patients in a PACU. Following administration of IV caffeine, RASS scores increased and no adverse respiratory events were noted following caffeine administration. The data suggested that IV caffeine may enhance speed of recovery from general anesthesia. Warner and colleagues' study provides preliminary evidence that coffee consumption may increase speed of recovery. Once again, no studies have examined whether providing coffee to patients postoperatively would decrease the length of stay in the PACU compared to not providing coffee.

Research Plan

• Study Design

A randomized, non-blinded, controlled study will be conducted, with two arms. Subjects will be randomized into one of the two following arms:

- Arm 1: Subjects will receive coffee while in the PACU
- Arm 2: Subjects will NOT receive coffee in PACU
- Setting for the study

The study will take place in the Bethesda North Minimally Invasive Surgery Center. This unit consists of 3 operating rooms and 7 postoperative recovery bays. The team members on this unit provide care for patients undergoing minimally invasive outpatient procedures including (but not limited to) Herniorrhaphy Repairs, Laparoscopic Cholecystectomies, Lipoma Removals, Hysteroscopies, Uterine Ablations, Bladder Slings, Female Sterilization, Breast Reductions and Augmentations, and other Plastic Surgery. There are approximately 10-20 surgeries performed in this setting each day. We are a 3 OR Suite facility with 6 Pre-Op Bays and 7 Recovery Bays.

In April 2022, the Bethesda Surgery Center was added as a second recruitment site. This unit consists of 4 operating rooms and 8 postoperative recovery bays. The team members on this unit provide care for patients undergoing minimally invasive outpatient procedures including (but not limited to) Herniorrhaphy Repairs, Laparoscopic Cholecystectomies, Hemorrhoidectomies, Lipoma Removals, Eye Muscle Repair, Breast Reductions and Augmentations, Abdominoplasty, and other Plastic Surgery. There are approximately 10-20 surgeries performed in this setting each day. We are a 4 OR Suite facility with 6 Pre-Op Bays and 8 Recovery Bays.

• Participants

This study will enroll 300 subjects who meet the inclusion/exclusion criteria.

Inclusion criteria:

- 1. 18 years old or older
- 2. Admitted to Bethesda North Minimally Invasive Surgery Center or the Bethesda Surgery Center
- 3. Reports to consume at least one cup of coffee a day for at least 5 days in a week

Exclusion Criteria

- 1. History of PONV
- 2. Pre-existing cardiac arrhythmias
- 3. History of seizure disorder
- 4. Pregnant

Withdraw Criteria (patients who meet inclusion/exclusion criteria and consent to participate, but then develop one of these criteria, will be removed from the study)

- 1. Participants in the intervention arm who fail to drink at least 50 ml of coffee
- 2. Participants in the intervention arm who experience PONV prior to coffee consumption
- 3. Participants in the control arm who experience PONV prior to or during consenting process (consenting process will stop if patient begins experiencing PONV)

Sample Size Determination: A power analysis was conducted using G*Power (version 3.1.9.2). The primary outcome variable (length of stay) was used with a small-medium

effect size (0.3), power of 0.8, and level of significance 0.05. It was determined that 139 patients would be needed in each group, for a total sample size of 278 patients. Therefore, we plan to enroll approximately 300 patients to allow for missing data and patient withdrawals.

• Data Collection

Before the study begins, the study staff will provide education to all of the nurses working in the department involved in patient care. This education will include information about the study design, the intervention, and the inclusion/exclusion criteria.

Patients who meet the inclusion criteria will be approached by a member of the study team. The study team member will describe the study and answer any questions the patient has. If the patient is interested in enrolling in the study, they will be asked to review and sign an Informed Consent Form and a HIPAA Authorization Form. Personal health information, including name and date of birth, are recorded on the informed consent form and/or HIPAA Authorization Form.

After the patient provides written informed consent, the study team member will remove the next envelope out of a box of prefilled and sealed opaque envelopes. The envelope will provide the Subject ID number to be used on all study-related documentation and the study Arm that the patient has been randomized to.

• Intervention or experimental aspect of the study

Patients randomized to Arm 1 will receive coffee in a Styrofoam cup at a temperature of 125 degree Fahrenheit or less (Brown & Diller, 2008). Coffee will be offered to the patient in the PACU once the patient's gag reflex has been restored following their procedure. Volume of estimated coffee consumption will be measured using a sample scale (with a maximum of 300mL of coffee offered). Patients randomized to Arm 2 will not be offered coffee while in the PACU.

A data collection form will accompany patient to the PACU designating them as a study participant. Data will be recorded directly on this form and collected by a study team member after the patient is discharged.

Independent variable:

• Whether patient consumed part or all of the coffee in the PACU or not

Dependent variables:

- o Primary outcome variable Patient's LOS in the PACU
- Secondary outcome variables:
 - Whether the patient experienced PONV
 - Patient satisfaction

Potential confounding variables:

- o How many minutes after entering PACU patient consumed coffee
- o How much coffee patient consumed

• Statistical Analysis

Data will be recorded on paper data collection forms with only subject ID and no identifiers. Data from these forms will be entered into a password protected database. Only study team members will have access to the database. No personal information will be entered into the electronic database. Data will undergo range checks when entered into the database, and quality control procedures will be performed to ensure accuracy of the data in the electronic database.

Statistical analyses will be performed using SPSS statistical software. Descriptive statistics (frequencies for categorical data; means and standard deviations and ranges for continuous data) will be used to describe the sample. The following analyses will be performed to address each hypothesis:

Hypothesis 1: Patients who self-identify as coffee drinkers who receive coffee postoperatively will experience a shorter length of stay in the PACU compared to patients who self-identify as coffee drinkers and do not receive coffee postoperatively.

To compare the effects of the intervention, an independent samples t-test will be used to compare mean length of stay in the PACU for patients who received coffee to the mean length of stay in the PACU among patients who did not receive coffee. A level of significance of α =0.05 will be used.

Hypothesis 2: Patients who self-identify as coffee drinkers who receive coffee postoperatively will experience a lower occurrence of postoperative nausea and vomiting in the PACU compared to patients who self-identify as coffee drinkers and do not receive coffee postoperatively.

To compare the effects of the intervention, a Chi Square test will be used to compare occurrence of postoperative nausea and vomiting for patients who received coffee to patients who did not receive coffee. A level of significance of α =0.05 will be used.

Hypothesis 3: Patients who self-identify as coffee drinkers who receive coffee postoperatively will report higher patient satisfaction compared to patients who self-identify as coffee drinkers and do not receive coffee postoperatively.

To compare the effects of the intervention, an independent samples t-test will be used to compare mean patient satisfaction for patients who received coffee to the mean patient satisfaction among patients who did not receive coffee. A level of significance of α =0.05 will be used.

Ethical Considerations

• Informed consent

All study staff will complete CITI training. A study staff member will meet with potentially eligible patients and describe the study and answer any questions. If the patient is interested and meets all the inclusion/exclusion criteria, the study staff will review the *Informed Consent Form* and *HIPAA Authorization* and obtain written informed consent. Patients will receive a copy of their signed Informed Consent form and HIPAA Authorization.

Informed Consent forms and HIPAA Authorizations will be stored in a locked cabinet that only study staff will have access to. After the study closes, the signed Informed Consent forms and HIPAA forms will be boxed and sent to off-site storage and securely stored for 10 years. At that time, the hard copy forms will be shredded.

• Privacy information

Personal identifiers will not be recorded on data collection forms or the electronic database of final data. Hard copy data collection forms will be stored in locked cabinets that only study staff will have access to. Electronic data will be stored on a password-protected folder on the U drive. Only study staff will have access to the electronic study documents. After data analysis and dissemination is completed, hard copy forms will be boxed and sent to secure storage for 10 years at which time they will be shredded. After data analysis and dissemination, electronic data and forms will be de-identified and transferred to a password-protected flash drive which will be sent to secure storage for 10 years at which time they will be sent to secure storage for 10 years at which time the sent to secure storage for 10 years at which will be sent to secure storage for 10 years at which time the sent to secure storage for 10 years at which time it will be destroyed.

Cost/Budget

There will be no costs to conduct this study and no additional charges to patients.

Estimated Period of Time to Complete Study	
When will study begin?	April 1, 2018
Protocol Development	1 month
Completed	
Scientific Review	2 weeks
Admin Review Time	2 weeks
IRB Approval	6 weeks
Data collection	3 months
Data analysis	2 months
Presentation development	1 month
(if applicable)	
Manuscript Development	3 months
(if applicable)	

Journal submission process (if applicable)	6 months
Study closure	1 month

• When and how will results be disseminated?

Results will be disseminated internally to the TriHealth perioperative leadership team and system-wide through the TriHealth Research Council. Results will be disseminated nationally through presentation at a professional organization conference. Finally, results will be disseminated nationally and internationally by publication in a relevant peer-reviewed journal.

References

Brown, F., & Diller, K.R. (2008). Calculating the optimum temperature for serving hot beverages. *Burns*, *34*, 648-657. DOI: 10.1016/j.burns.2007.09.012

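### Nausea or vomiting before coffee, itself the Hypothesis 2 outcome, removes randomised patients from the coffee arm only, which biases that comparison toward coffee

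*Combined protocol and SAP*

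**What the plan says.** All references are to the combined protocol and SAP.

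- **Withdraw Criteria (Participants).** Consented patients who were eligible "but then develop one of these criteria, will be removed from the study". Criterion 1 covers "Participants in the intervention arm who fail to drink at least 50 ml of coffee". Criterion 2 covers "Participants in the intervention arm who experience PONV prior to coffee consumption". Criterion 3 covers "Participants in the control arm who experience PONV prior to or during consenting process".
- **Order of events (Data Collection).** "After the patient provides written informed consent, the study team member will remove the next envelope". The envelope holds the arm, so nobody has an arm until consent is complete.
- **Timing of coffee (Intervention section).** It is offered in the PACU after the gag reflex returns, which leaves an interval between randomisation and coffee.
- **Hypothesis 2 (Statistical Analysis).** A chi-square test at 0.05 compares PONV in the PACU between patients who did and did not receive coffee. No starting time is set for counting PONV, and nothing says how PONV before coffee is handled. The independent variable is coffee consumed, not assigned arm. No intention-to-treat analysis is described.
- **Timing of consent.** Criterion 3 adds that the "consenting process will stop if patient begins experiencing PONV", which implies consent after surgery. The Intervention section says "A data collection form will accompany patient to the PACU designating them as a study participant", which implies consent before it.

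**The concern.** Criterion 2 selects one arm on the outcome being tested. Every patient it removes is a Hypothesis 2 event, and every one comes from Arm 1. Criterion 3 looks like its counterpart but is not: the period it covers ends before the envelope is opened. A control who becomes nauseated after randomisation stays in and counts as an event.

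The trial could therefore report less PONV with coffee when coffee does nothing. A larger sample would make that false result more likely. Criterion 1 can act in the same direction, because a nauseated patient may not drink 50 ml. Both criteria also remove patients from the length-of-stay and satisfaction comparisons, so the primary comparison is not between the groups as randomised.

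**Working it through.** **The plan's own figure.** The sample size is for length of stay: effect size 0.3, power 0.8, significance level 0.05, 139 per group. The t-test calculation gives 138.07, so 139, if one-sided, and 175.4, so 176, if two-sided. The stated figure is therefore reproduced only by a one-sided test. No PONV rate, effect or power is given for Hypothesis 2.

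**Model.** Let p be the true PONV risk, the same in both arms (inert coffee), and f the share of PONV that falls between randomisation (or PACU entry, if later) and coffee. Both are assumptions. I take 150 per arm from the planned enrolment of about 300. Each Arm 1 patient is then:

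- removed, with probability pf;
- kept with PONV, with probability p(1 − f);
- kept without PONV, with probability 1 − p.

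Analysed Arm 1 risk = p(1 − f)/(1 − pf). Arm 2 risk = p.
False difference = p − p(1 − f)/(1 − pf) = pf(1 − p)/(1 − pf), which is positive for any f above 0.

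Example with p = 20%, f = 25%: 0.15/0.95 = 15.8% against 20%, with 150 × 0.20 × 0.25 = 7.5 patients removed on average. At f = 2, 5, 10 and 50% the analysed Arm 1 risk is 19.7, 19.2, 18.4 and 11.1%.

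**Chance of a significant chi-square favouring coffee** (two-sided 0.05, so nominally 2.5% in this direction; no continuity correction; 1,000,000 simulated trials per cell; repeat runs agree to about 0.1 point):

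| f | p = 5% | p = 10% | p = 20% | p = 30% |
|---|---|---|---|---|
| 0 | 2.4% | 2.5% | 2.5% | 2.5% |
| 2% | 2.6% | 2.8% | 3.0% | 3.0% |
| 5% | 3.0% | 3.4% | 3.8% | 3.9% |
| 10% | 3.8% | 4.5% | 5.5% | 6.1% |
| 25% | 7.0% | 10.2% | 15.3% | 18.9% |
| 50% | 18% | 33% | 54% | 68% |

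This one-directional error reaches 5% at about f = 17, 12, 9 and 8% for the four risks. The total two-sided error is then about 6%, because the opposite tail shrinks. Keeping all randomised patients by assigned arm returns 2.4% to 2.5% in every cell.

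**Length of stay.** Suppose PONV adds δ = 0.5 to 1 SD to stay (assumption). The bias in SD units is δ·pf(1 − p)/(1 − pf), divided by √(1 + δ²p(1 − p)).

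- p = 10%, f = 50%, δ = 0.5: 0.5 × 0.0474/1.011 = 0.02.
- p = 30%, f = 50%, δ = 1: 0.1235/1.1 = 0.11, against a planned effect of 0.3.

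Two-sided error across that range is 5.4% to 15.4%. At f = 10% the bias is at most 0.02 SD and the error is 5.0% to 5.3%.

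**The case against.** The strongest reply is that the effect may be small. If consent is taken in the PACU, as the stopping note in criterion 3 suggests, early PONV is screened out before any envelope is opened, equally for both future arms. Only the gap from envelope to coffee is left, and f could be a few percent, where the error is barely above nominal. The exclusion "History of PONV" may also make the higher risks less likely. All of this stands as a limit on size. It does not remove the asymmetry, and the accompanying data form points toward earlier consent and a larger f.

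A second reply is that receiving coffee may be shorthand for the assigned arm. Under the current rules the two coincide among patients kept, because those who do not drink are removed and controls are not offered coffee. That is right: the grouping adds no error today. It matters only if criterion 2 is deleted while the grouping stays.

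Third, a common landmark in both arms would also remove the Hypothesis 2 bias, with more power. That is correct; which analysis leads is a choice of the question to be answered. The length-of-stay bias is also conditional on an effect of PONV on stay that the documents do not quantify.

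**Conclusion.** The concern holds. As written, PONV between randomisation and coffee is deleted in Arm 1 and counted in Arm 2, and nothing else in the plan corrects this. Confidence in the existence and direction of the bias is high, because both follow from the text for any f above 0.

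The size cannot be fixed from the documents. It runs from negligible at f = 2% to a false finding in 18% to 68% of null trials at f = 50%, given 150 per arm and risks of 5% to 30%. Low f fits consent in the PACU; high f fits consent before surgery. Hypothesis 2 is secondary, but it has its own test at 0.05. Bias in the primary outcome is possible but depends on PONV lengthening stay. The change is required because the comparison is invalid by construction and can be repaired cheaply.

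**What to change.** 1. Stop using criteria 1 and 2 to remove data from the main analysis. Both must go, since a nauseated patient who does not drink also falls under the 50 ml rule. Whether such a patient is offered coffee stays with the clinical team; only data handling changes.
2. Analyse all randomised patients by assigned arm for length of stay, PONV and satisfaction, and reword the tests and the independent variable to match. Deleting criterion 2 alone would make matters worse: if early-PONV Arm 1 patients were counted as not receiving coffee, the error favouring coffee would be about 5.5% to 12% at f = 10%, 15% to 51% at f = 25% and 47% to 99% at f = 50%.
3. Count PONV in both arms from the later of randomisation and PACU entry to PACU discharge.
4. Add a supportive Hypothesis 2 analysis from a common landmark, the time coffee could first be offered, recorded in both arms.
5. Report patients who drank at least 50 ml only as a labelled secondary analysis.
6. State when consent and randomisation occur, and reconcile criterion 3 with the envelope order and the accompanying form.
7. For patients already removed: a recorded criterion 2 removal in the PACU shows PONV = yes, so restore it to Hypothesis 2. For length of stay, satisfaction and criterion 1 removals, use whatever outcomes were recorded, report the number missing by arm, and bound Hypothesis 2 by setting missing PONV to all yes and all no.

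**Cost.** Wording, completed forms for patients now dropped, and one landmark time per patient.

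*Power for length of stay.* If a share q of Arm 1 does not drink and only drinkers benefit, the effect becomes 0.3(1 − q): 0.285, 0.27 and 0.255 at q = 5, 10 and 15%. At 150 per arm, one-sided power is 79, 75 and 71%, against 82, 81 and 80% with removal as now; two-sided it is 69, 64 and 60%. Holding 80% one-sided needs 153, 171 and 191 per group. If only 0.5% to 3% do not drink, one-sided power stays at 81% to 82%. Patients under 50 ml for other reasons add to the dilution; their share is not given.

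*Power for Hypothesis 2.* If coffee halves later PONV (assumption) and p = 20%, power at f = 2, 5, 10, 25 and 50% is 67, 63, 58, 42 and 21% over the whole period, against 68, 66, 64, 55 and 38% from the landmark.

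### The 139 per group comes from a one-sided calculation that the plan never declares; a two-sided 0.05 t-test at that size has about 70% power, not 80%

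*Combined protocol and SAP*

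**What the plan says.** The Sample Size Determination paragraph (Research Plan, Participants) uses length of stay in the PACU as the outcome, cites G*Power 3.1.9.2, and gives its inputs as "effect size (0.3), power of 0.8, and level of significance 0.05". It then states: "It was determined that 139 patients would be needed in each group, for a total sample size of 278 patients". Planned enrolment is raised to about 300 to cover missing data and withdrawals.

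The Statistical Analysis section says for Hypothesis 1 that "an independent samples t-test will be used to compare mean length of stay in the PACU" between patients who received coffee and those who did not, followed by "A level of significance of α =0.05 will be used". The same significance sentence closes the chi-square paragraph (Hypothesis 2) and the satisfaction t-test paragraph (Hypothesis 3).

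Hypothesis 1 is worded directionally: coffee recipients "will experience a shorter length of stay in the PACU compared to patients who self-identify as coffee drinkers and do not receive coffee postoperatively". Nowhere does the document say whether any test is one-sided or two-sided.

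**The concern.** A t-test at 0.05 with no further qualification is normally run and reported two-sided, and it is what an analyst following the Statistical Analysis section would do. The sample size agrees with the stated power only if the test is one-sided. The stated power and the analysis as ordinarily read therefore describe two different tests.

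This affects the primary outcome in three ways:

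- **If the test is run two-sided,** the chance of missing the planned effect is about 30% rather than 20%, and a null result would be read against power that the trial does not have.
- **If the test is run one-sided,** the chance of falsely concluding that coffee shortens stay is 5%, twice the 2.5% that a two-sided 0.05 test allows in that direction, and the reader has not been told.
- **If the choice stays open,** a favourable difference with a two-sided p-value between 0.05 and 0.10 could be called significant or not after the data are known. The trial is non-blinded, so settling this in advance matters more.

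**Working it through.** **Inputs.** From Sample Size Determination: effect size 0.3, power 0.80, significance level 0.05, equal groups. From Statistical Analysis: independent-samples t-test. The effect size is taken as the standardised mean difference d, because no standard deviation or difference in minutes is given.

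**Step 1: sample size by the normal approximation.** Per group, n = 2(z_alpha + z_power)² / d², with z_power = 0.8416.

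- One-sided 0.05: 2 × (1.6449 + 0.8416)² / 0.09 = 2 × 6.183 / 0.09 = 137.4, so 138.
- Two-sided 0.05: 2 × (1.9600 + 0.8416)² / 0.09 = 2 × 7.849 / 0.09 = 174.4, so 175.

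**Step 2: exact calculation (noncentral t, the method the cited software uses).**

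| Test | n per group | Rounded up | Total |
|---|---|---|---|
| One-sided 0.05 | 138.07 | 139 | 278 |
| Two-sided 0.05 | 175.38 | 176 | 352 |

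The one-sided row reproduces the plan's figure exactly. Two-sided testing at 0.10 also gives 139 (138.06 before rounding) but contradicts the stated 0.05. Other candidates do not give 139: a rank-sum test needs 145 one-sided or 184 two-sided under normality, and 160 or 203 at its minimum efficiency; a two-sided paired t-test needs 90.

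**Step 3: power at the planned size, d = 0.3.** The normal approximation for 139 per group is 0.3 × √(139/2) = 2.501. Two-sided, 2.501 − 1.960 = 0.541, which gives 70.6%. One-sided, 2.501 − 1.645 = 0.856, which gives 80.4%. The exact values are:

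| Analysed per group | Two-sided 0.05 | One-sided 0.05 |
|---|---|---|
| 139 | 70.3% | 80.2% |
| 150 (all 300, no losses) | 73.6% | 82.8% |
| 176 | 80.1% | 87.8% |

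**Step 4: effect detectable with 80% power, two-sided 0.05.** d = 0.337 at 139 per group and 0.325 at 150 per group.

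**Step 5: shortfall.** For 80% power two-sided at d = 0.3, the evaluable shortfall is 352 − 278 = 74. The plan allows for (300 − 278)/300 = 7.3% loss. With the same allowance, 352 evaluable patients would mean enrolling 352 / (278/300) = 379.9, about 380.

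**The case against.** The best defence is that a one-sided test was intended. The hypothesis is directional, it is repeated directly above the t-test, and the sample size matches the one-sided answer exactly. On that view the sum is right, one word is missing, and a one-sided 0.05 test has exactly the 5% error rate that the plan states.

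Much of this stands. The 139 is not a miscalculation, and the directional hypothesis probably explains the software setting. It is also fair that a one-sided 0.05 test does not exceed the declared alpha, and that the 70% figure is conditional on two-sided testing.

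What does not follow is that the analysis is committed to one side. The Hypothesis 1 paragraph compares means at 0.05 and gives no one-sided rejection rule. Hypothesis 2 is just as directional, yet it is assigned a chi-square test, which is non-directional, with the identical significance sentence. That does not settle the sidedness of the t-test, but it shows that in this document directional wording does not by itself signal a one-sided test.

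Nor does enrolling 300 close the gap. Two-sided power is still 73.6% with no losses at all, and the 22 extra patients are already set aside for missing data and withdrawals.

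**Conclusion.** The concern holds. The stated 80% power belongs to a one-sided 0.05 test that the plan does not declare. On the ordinary two-sided reading, power for d = 0.3 is 70.3% at 139 per group and at most 73.6% with all 300 analysed; 80% power is reached only for d of about 0.34 at 139 per group. The fault is an undeclared choice that makes the primary power statement wrong on its usual reading, not an arithmetic slip. It should be corrected before analysis.

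The conclusion assumes that 0.3 is a standardised mean difference, which the small-to-medium label and the exact one-sided match support. It also assumes equal groups and the usual t-test conditions.

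**What to change.** Preferred: state in the Hypothesis 1 analysis that the t-test is two-sided at 0.05, and reword the sample-size sentence to say that 139 evaluable patients per group give 70% power for an effect size of 0.3 and 80% power for 0.34, at two-sided alpha 0.05.

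Alternative, if one-sided testing is truly intended: say so, with the reason, in both the Sample Size Determination paragraph and the Hypothesis 1 analysis, and report that the 278 rests on one-sided alpha 0.05.

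Either way, say in the sample-size text that 0.3 is a standardised mean difference. The satisfaction t-test under Hypothesis 3 has the same omission and can be clarified at the same time.

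The core change is two sentences. Neither option needs more patients; the price of the preferred one is a less favourable stated power. Only if the sponsor wishes to keep 80% power at 0.3 with a two-sided test would the trial need 352 evaluable patients.
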